**Analysis of the overall success rate at 18 months, giving equal weight to each centre:**

This analysis will be provided on the mITT (cf. section 7.3 for further details).

**8.6.3. Analysis of other secondary endpoints****Correlation analyses between concentrations in the blood (AUC) and CSF and the success rate**

These analyses will be performed by [REDACTED]. A separate statistical analysis plan will be prepared by [REDACTED] for these analyses. Cf. protocol, Section 9.6.3 for further details.

**Correlation between concentrations in the blood (AUC) and CSF and the occurrence of AEs**

These analyses will be performed by [REDACTED]. A separate statistical analysis plan will be prepared by [REDACTED] for these analyses. Cf. protocol, Section 9.6.3 for further details.

**Changes in the rate of favourable outcomes over time**

Changes in the success rate over time (at 6, 12 and 18 months) for stage 2 patients on one hand, and for stage 1 and intermediate-stage patients on the other hand, will be studied using a logistic mixed model for repeated measures, based on the GLIMMIX SAS procedure, using the following specifications:

- estimation method = Pseudo-Likelihood (METHOD=RSPL)
- binary endpoint = success rate (with events coded as '1' and failures coded as '0')
- distribution = binary
- link = logit
- unique patient id defined as class variable
- visit defined as class variable, with reference value = 6-month visit
- unstructured covariance structure

Odds ratio, their 95% CI and the corresponding p-value will be displayed for the following comparisons of success rate: 12 months versus 6 months, 18 months versus 6 months, and 18 months versus 12 months. This analysis will be provided on the mITT. Algorithms used to derive success rates at 6, 12 and 18 months are described in [Section 10](#).

#### **Time to proven and definitive failure in Patients with Stage 2 HAT**

This endpoint will be analysed using the Kaplan-Meier approach in order to estimate, at each follow-up visit (EoH, 3, 6, 12 and 18 months) the cumulative rate of proven failures. The Kaplan-Meier curve will be presented. The number of events and censoring will be provided at each visit (EoH, 3, 6, 12 and 18 months). Survival probability at each visit (EoH, 3, 6, 12 and 18 months) will be calculated with its 95% CIs using the log-log transformation. This analysis will be provided on the mITT.

A trend test (Cochran-Armitage test) will be used to assess the relationship between success rate at 18 months (as well as 12 months) and ordered class of disease progress (see Table 1): stage 1 versus intermediate stage versus stage 2.

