**Table 5 - Populations Used in the Analyses**

Type	Aim	Definition
Primary: modified intent-to-treat (mITT) patients	Primary analysis	All patients who received at least one tablet of acoziborole, excluding patients who fled the region due to armed conflict or natural disaster, or due to force majeure, and for whom no post-treatment data are available. These patients will be included in the population as failures for an “all-patient” sensitivity analysis.
All patients	Safety analyses and sensitivity analyses on efficacy	All patients who received at least one tablet of acoziborole. There will be no exceptions to this rule.
Secondary: evaluable patients	Sensitivity analyses on efficacy	Patients in the mITT population for whom at least one lumbar puncture is available (at 6, 12 or 18 months), and excluding patients who died for reasons clearly unrelated to efficacy or safety, or who fled the region due to armed conflict or natural disaster.
Secondary: per-protocol patients	Sensitivity analyses on efficacy	Patients in the mITT population with no major protocol violations. Major violations will be described by patient, and exclusion will be decided during the data review.

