##### **Other Secondary Analyses**

- The correlation between acoziborole concentrations in the blood and CSF and the success rate in late-stage patients will be determined using logistic regression with success or failure as the response (dependent variable) and two covariables (explanatory variables): blood and CSF concentrations.
- The correlation between acoziborole concentrations in the blood and CSF and the occurrence of AEs in late-stage patients will be determined using logistic regression with the occurrence of AEs during hospitalisation as the response (dependent variable) and two covariables (explanatory variables): blood and CSF concentrations.
- Changes in the rate of favourable outcomes over time for late-stage patients on the one hand, and for early- and intermediate-stage patients on the other hand, will be studied using the mixed model for repeated measures (Glimmix).
- Time to proven relapse will be analysed in each cohort using the Kaplan-Meier approach in order to estimate, at each follow-up visit, the cumulative rate of proven failures. Patients lost to follow-up will be censored at the last available visit, unless the outcome at that visit was failure.

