## 5. ANALYSIS SETS AND SUBGROUPS

The analysis sets are defined below:

- **Set of screened HAT positive patients:** All HAT positive patients who signed the informed consent. To be noted that after the 1st DSMB meeting, recruitment of stage 1 and intermediate stage HAT patients was authorized. That will trigger a modification of the initial screened set.
- **Treated set:** all patients who received at least one tablet of acoziborole.
- **Modified Intention-To-Treat (mITT):** All patients who received at least one tablet of acoziborole, excluding patients (\*) who fled the region due to armed conflict or natural disaster or due to force majeure (\*\*) and for whom no failure was detected early (parasite, needs for rescue medication, death or more than 50 WBC/µL in CSF at M6) and no data are available at M12 and M18 due to armed conflict, natural disaster or force majeure affecting the site.
- **Evaluable patients:** Modified Intent-to-treat patients (mITT) and excluding:
  - Patients lost to follow-up at 18 months (for primary efficacy endpoint and secondary efficacy outcome at 18 month), patients lost to follow-up at 12 months (for secondary efficacy outcome at 12 month), patients lost to follow-up at 6 months (for secondary efficacy outcome at 6 month), except those who were a failure before being lost to follow-up (cf. [Section 7.7](#) for programming rules).
  - Patients with no post-treatment lumbar puncture (i.e. patients who refused all lumbar puncture after treatment and who were not a failure)
  - Patients who died for reasons clearly unrelated to efficacy or safety or disease evolution (\*\*).
  - Early consent withdrawal (before M6, i.e. no planned visit attended after 3-month visit).
- **Per Protocol Set (PPS):** Modified Intent-to-treat patients (mITT) with no major protocol deviations (\*\*\*). Major deviations will be described by patient, and exclusion will be decided during the data review (cf. [Section 8.2](#)).

Notes:

(\*) These patients will be included in the Treated set population as failures.

(\*\*) This will be reviewed during data review meeting (e.g. review of comments and reasons of early discontinuation in end-of-study form).

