### 6.3. Other secondary efficacy endpoints

#### Time to proven and definitive failure in Patients with Stage 2 HAT

The starting point is administration of acoziborole. The time of failure is the time of the first objective evidence of sustainable failure defined as:

- Death for any reason (at any time on or after administration of acoziborole)
- Decision to use rescue medication (at any time on or after administration of acoziborole)
- Observation of trypanosomes in any body fluid at M6, M12 or M18
- a CSF WBC above 50 / $\mu$ L at 6 months followed by a confirmation of failure defined as:
  - CSF WBC above 20 / $\mu$ L at 12 months, and/or
  - CSF WBC above 20 / $\mu$ L at 18 months, and/or
  - Sign and symptoms evoking a relapse at M12, and/or
  - Sign and symptoms evoking a relapse at M18.
- a CSF WBC above 20 / $\mu$ L at 12 months followed by a confirmation of failure defined as:
  - CSF WBC above 20 / $\mu$ L at 18 months, or
  - Sign and symptoms evoking a relapse at M18.
- a CSF WBC above 20 / $\mu$ L at 18 months

This endpoint will be derived as follows:

- Proven and definitive failure patients:
  - Event (cf. definition above)
  - Time = Theoretical time of the follow-up visit (i.e. day 15 for EoH visit, day 91 for M3 visit, day 183 for M6 visit, day 365 for M12 visit, day 548 for M18 visit)
- Non-failure patients (i.e. proven and definitive failure free):
  - If CSF WBC > 20/ $\mu$ L at 12 months and CSF WBC < 20/ $\mu$ L at 18 months:
    - Censoring at M12 visit
    - Time = Theoretical time of M12 visit (i.e. at day 365)
  - Otherwise:
    - Censoring at the last visit free from proven and definitive failure
    - Time = Theoretical time of the follow-up visit (i.e. day 15 for EoH visit, day 91 for M3 visit, day 183 for M6 visit, day 365 for M12 visit, day 548 for M18 visit)

Note: Unlike the preceding endpoints, a patient cannot be a proven and definitive failure at a given time point and a success at a subsequent endpoint. Consequently, a patient with a CSF WBC above 20/ $\mu$ L at 12 months and below 20/ $\mu$ L at 18 months will be censored at 12 months. A patient lost to follow-up is a patient censored at the last available visit if there is no evidence of failure up to the last available visit. A success at 18 months (last assessment) is a patient censored at 18 months, i.e. with no evidence of failure up to 18 months.

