**9.1.4. List of outputs for ICH Section 14.2.3 (Other efficacy endpoints)****14.2.3 Other efficacy endpoints**

14.2.3.1: Changes in the rate of favorable outcomes over time in patients with stage 2 HAT (mITT)

14.2.3.2: Changes in the rate of favorable outcomes over time in stage 1 and intermediate-stage patients (mITT)

14.2.3.3: Kaplan-Meier analysis of time to proven and definitive failure in Patients with Stage 2 HAT (mITT)

14.2.3.3.1: Figure: Kaplan-Meier curve

14.2.3.3.2: Table: Survival probabilities

14.2.3.4: Descriptive analysis and trend test of success rates at 18 months: stage 1 versus intermediate stage versus stage 2 (mITT)

14.2.3.5: Descriptive analysis and trend test of success rates at 12 months: stage 1 versus intermediate stage versus stage 2 (mITT)

14.2.3.6: Descriptive analysis and test of homogeneity of success rates at 18 months by center - Stage 2 patients (mITT)

14.2.3.7 Forest plot of success rate at 18 months by center - Stage 2 patients (mITT)

14.2.3.8: Descriptive analysis and test of homogeneity of success rates at 18 months by center - Stage 1 and intermediate-stage patients (mITT)

14.2.3.9 Forest plot of success rate at 18 months by center - Stage 1 and intermediate-stage patients (mITT)

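### The time-to-failure curve is run on the mITT, which removes displaced patients partly according to outcome and discards follow-up that the endpoint's own rule would censor; the effect is small and runs against acoziborole

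*SAP*

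**What the plan says.** SAP 8.6.3 estimates cumulative proven failure at EoH, M3, M6, M12 and M18. The survival probability at each visit "will be calculated with its 95% CIs using the log-log transformation. This analysis will be provided on the mITT". Output 14.2.3.3 in SAP 9.1.4 is likewise labelled mITT, and no Treated-set version is listed. Sensitivity analysis #3 in SAP 8.6.1.2 uses the Treated set, but for the success rate only.

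SAP 5 excludes from the mITT treated patients who were displaced "and for whom no failure was detected early" (parasite, rescue medication, death, or more than 50 WBC/µL in the CSF at M6) and for whom "no data are available at M12 and M18 due to armed conflict, natural disaster or force majeure affecting the site". A note to that section, marked with a single asterisk, puts the excluded patients in the Treated set as failures.

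The endpoint has its own rule for losses. SAP 6.3: "A patient lost to follow-up is a patient censored at the last available visit if there is no evidence of failure" up to that visit. Protocol 9.6.3: "Patients lost to follow-up will be censored at the last available visit", unless that visit already showed failure.

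The protocol's mITT is narrower. Table 5 drops displaced patients who left because of conflict or disaster "or due to force majeure, and for whom no post-treatment data are available", and Protocol 8.1 adds a similar no-data condition. SAP 11, which lists departures from the protocol, does not mention the broader SAP definition.

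**The concern.** For the 18-month proportion, a patient with no late outcome must be called a success, called a failure or left out, so an exclusion rule has a purpose. A Kaplan-Meier curve needs no such choice: a patient seen free of failure to M6 and then displaced contributes to the risk set up to M6 and is censored there.

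On the mITT that patient disappears, while a displaced patient with an early failure remains. Membership of the analysis set then depends partly on something observed after treatment, and events are kept while matching failure-free time is removed. The curve serves a stated secondary objective, the time course of failure in late-stage patients. What is at stake is a slight overstatement of failure, some lost precision, and disagreement between the analysis set and the censoring rule written for the same endpoint.

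**Working it through.** **1. The plan's own figures.** The documents give no numerical target for this curve. The sample is 155 late-stage patients plus a provision of 7 for displaced patients: 155 + 7 = 162 (5% of 155 is 7.75; the plan takes 7). Recomputed Jeffreys intervals match the plan: 138/155 gives 83.4–93.2% and 146/155 gives 89.7–97.1%. These two scenarios have 17 and 9 failures, used in step 4.

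**2. Who stays and who goes**, reading SAP 5 against the event definition in SAP 6.3:

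| Displaced patient | In mITT? | Role in the curve |
|---|---|---|
| Death, rescue decision, or trypanosomes at M6 | Yes | Event |
| CSF WBC > 50 at M6, never confirmed | Yes | Censored |
| No early failure, M12 data exist | Yes | Followed as observed |
| No early failure, no M12 and M18 data | No | Observed visits discarded; SAP 6.3 would censor |

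The selection works through the first and last rows. The time lost ends at about M6.

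**3. Direction.** Each visit contributes the factor 1 − d/r, with d events among r at risk. Removing failure-free patients leaves every d unchanged and lowers r up to their last visit. Cumulative failure can therefore only rise or stay equal. Where d = 0 at every visit so far, nothing changes.

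**4. Gap between the two curves on the same data.** Assumption: 7 of 162 removed, so mITT n = 155.

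- All failures at M6, removed patients last seen at M6: 9/162 = 5.56% (censored) against 9/155 = 5.81% (mITT), gap 0.25 points; 17/162 = 10.49% against 17/155 = 10.97%, gap 0.47 points.
- Failures spread 3/3/3 over M6, M12 and M18, removed patients last seen at M6: 1 − (159/162)(149/152)(146/149) = 5.73% against 5.81%.
- Failures spread 5/5/7: 1 − (157/162)(145/150)(138/145) = 10.84% against 10.97%.
- Removed patients last seen at M3 and no event by M3: gap 0.
- 15 removed instead of 7, last seen at M6: gap 0.16 to 0.97 points over the same patterns.

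**5. Average bias when displacement is unrelated to outcome.** Let f be true failure by M6 and D the number displaced after the M6 visit, with 155 + D treated. Expected failures are f(155 + D); D(1 − f) failure-free patients are deleted. On the mITT, M6 failure is approximately

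f(155 + D) / (155 + fD).

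Assume f = 4% and 8% failure at M18.

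- D = 7: 0.04 × 162 / 155.28 = 4.17%. The conditional risk after M6 is (0.08 − 0.04)/0.96 = 0.0417, so the M18 figure is 1 − 0.9583 × 0.9583 = 8.17%.
- D = 15: 0.04 × 170 / 155.6 = 4.37%, and 8.35% at M18.

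Simulation (1,500 trials of 162, displacement after M6 and independent of outcome), mean estimated 18-month failure:

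| True failure | Displaced | Censored | mITT |
|---|---|---|---|
| 6% | 4.3% | 6.04% | 6.13% |
| 6% | 20% | 5.97% | 6.44% |
| 11% | 4.3% | 11.04% | 11.19% |
| 11% | 20% | 11.05% | 11.89% |

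Under this assumption censoring is close to unbiased and deletion is biased upward.

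**6. The interval.** The log-log limits need ln(−ln S), which does not exist at S = 1. Before M6 only a death or a rescue decision counts as an event under SAP 6.3, so S = 1 at EoH or M3 is possible. The chance of no EoH event in 155 patients is 0.995^155 = 46% at an assumed early risk of 0.5%, and 0.99^155 = 21% at 1%. The Clopper-Pearson lower limit for 155/155 is 0.025^(1/155) = 97.6%.

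**The case against.** The strongest reply is that this hardly matters. The average bias at M6 is 0.17 points under the assumptions of step 5; the planned 95% interval for the 18-month rate at 89% success is 9.8 points wide. The loss of precision is about 2% of interval width, since √(162/155) = 1.02. Seven is a replacement provision, not a forecast. At 4% failure by M6, the chance that any of 7 displaced patients is a retained failure is 1 − 0.96^7 = 25%. The endpoint is secondary, no success rule hangs on it, and the neighbouring repeated-measures and by-centre analyses also use the mITT. All of this stands, and it sets the priority.

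It does not remove the inconsistency, because no other output covers the curve.

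Four stronger readings are tempting but not supported:

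- That displaced patients enter the curve only if they failed. Those with M12 data stay, and so do those with an unconfirmed M6 count above 50, who are not events.
- That the plan itself treats displacement as non-informative. No section says so. The plan excludes and replaces these patients, and counts them as failures in the Treated set. Independence from outcome is an assumption of this check.
- That an event-free EoH visit is likely. The illustrative chances are both below one half, and the documents support neither assumed risk.
- That every early visit is biased. Before the first event the two curves coincide.

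**Conclusion.** The point holds in a limited form. Inclusion in the set used for the Kaplan-Meier curve depends partly on outcome, and failure-free follow-up to about M6 is discarded against the censoring rule in SAP 6.3 and Protocol 9.6.3. Much of this comes from the SAP's mITT being broader than that in Protocol Table 5, a change SAP 11 does not record.

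The distortion overstates failure. With 7 patients removed and 9 or 17 failures it is 0 to 0.47 points, and zero before any event. The number displaced, when they were last seen and when failures occur are assumptions; the documents give none of them. More displacement would enlarge it. The primary success-rate analysis is not affected by this point. It is a low-priority improvement. The undefined log-log limit is a separate, minor presentation matter.

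**What to change.** Run the time-to-failure analysis (SAP 8.6.3 and output 14.2.3.3) on all Stage 2 patients in the Treated set. State expressly that, for this endpoint, displaced patients without failure are censored at their last failure-free visit and that the single-asterisk note in SAP 5 does not apply. That statement is essential: if only the set's name were changed, a programmer following the note could count 7 displaced patients as failures, adding 7/162 = 4.3 points, far more than the bias being removed. The mITT curve can be kept as a second output.

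Record the broader mITT definition in SAP 11 as a change from Protocol Table 5.

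At visits before the first event, report a Clopper-Pearson interval, a method SAP 7.4 already names, in place of log-log limits (97.6–100% for 155/155).

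The cost is a few sentences in the SAP and, if both curves are kept, one more output. No new data are needed.

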#### **Exploratory subgroups analysis:**

Descriptive analysis of the success rates at 18 months (i.e. primary and secondary endpoint at 18 months) and at 12 months will be provided on the following subgroup:

- "A" versus "B+C+D+E+F"
- "A" versus "B+C+D" versus "E+F"
- "A" vs "B" vs "C" vs "D" vs "E" vs "F" (i.e. on each subgroup).

A trend test (Cochran-Armitage test) will be used to assess the relationship between success rate at 18 months (as well as 12 months) and each subgroup (i.e. "A" vs "B" **vs "F"** vs "C" vs "D" vs "E", in this order).

#### **By-center analysis of the success rates at 18 months:**

Descriptive analysis of the success rate at 18 months on Stage 2 patients will be provided by centre. A test of homogeneity (likelihood-ratio test) will be performed. 95% Jeffreys CI will be provided. This analysis will be provided on the mITT (cf. section 7.3 for further details). In addition, a Forest plot will be presented to assess whether the heterogeneity is quantitative (dispersion around a central value) or qualitative (presence of very atypical centres).

The same analysis will be provided for the success rate at 18 months on Cohort 2 (Stage 1 + intermediate-stage patients).

## 8.7. Futility Analyses

As per protocol, Section 9.6.2: an independent DSMB will be appointed, among other things, to supervise and review the futility, as well as the safety data. The DSMB will make recommendations on study continuation based on all available information.

Note 1: all analyses, tables, figures and listings to be provided for futility analyses are described in the **DSMB charter**.

Note 2: futility analyses will be performed on the raw database (i.e. not on the CDISC compliant database).

### **First futility analysis:**

The first futility analysis will be performed once the first 20 stage 2 patients reach the 3-month visit. If the failure rate at Day 11 is significantly higher than the failure rate for melarsoprol (cf. Protocol, Reference 18) the study should be stopped for futility and for ethical reasons. The failure rate for melarsoprol at the end of treatment was 5% (4.8% for n = 6840). If 4 patients out of 20 are failures at Day 11 ( $p = 0.0159$  one-sided), then the DSMB should recommend stopping the study, unless the rate can be explained by exceptional circumstances.

Failure rate at Day 11 will be computed as described in the table below.

**Table 5 : Derivation rules for failure rate at Day 11 in patients with stage 2 HAT**

|  |  |
|--|--|
| Outcome at D11
for the 1 st and 2 nd
futility analysis | 
Patient is <math>\Rightarrow</math> Dead (any reason) <math>\Rightarrow</math> Failure (stop)
 
<math>\Downarrow</math>
 
Alive
 
<math>\Downarrow</math>
 
Patient requires rescue medication for HAT <math>\Rightarrow</math> YES <math>\Rightarrow</math> Failure (stop)
 
<math>\Downarrow</math>
 
NO rescue medication
 
<math>\Downarrow</math>
 
Evidence of trypanosomes in any body fluid at Day 11 <math>\Rightarrow</math> YES <math>\Rightarrow</math> Failure (stop)
 
<math>\Downarrow</math>
 
NO observed trypanosomes in any body fluid <math>\Rightarrow</math> YES <math>\Rightarrow</math> Success (Stop)
 |
|--|--|

### **Second futility analysis:**

The second futility analysis will be performed once 70 stage 2 patients reach the 3-month visit. The recommendation to stop the study should be made if 8 patients or more out of 70 are failures at the end of hospitalisation ( $p = 0.023$  one-sided).

### **Third futility analysis:**

The last futility analysis will be performed once 70 stage 2 patients reach the 6-month visit. The proven failure rate will be compared to the failure rate with melarsoprol at 6 months, which is around 20%. If the rate is significantly higher than 20%, i.e.  $\geq 22$  out of 70 patients ( $p = 0.016$ , one-sided), the DSMB should recommend stopping the study.

This analysis will be performed on the following analysis set: “**first 70 stage 2 treated patients**” (note: “first” is defined according to the date of treatment administration on D1).

Failure rate at 6 months will be computed as described in the table below.

